8.7 Day 29 ± 3 days

The following assessments will be performed at approximately Day 29 (\pm 3 days):

- 1. Vital Signs (temperature/pulse/supine blood pressure)
- 2. SpO₂
- 3. Physical examination (including weight)
- 4. 12-lead ECG (single)
- 5. Chest X-ray or CT scan
- 6. Clinical Laboratory tests
 - a. Hematology (Appendix A)
 - b. Serum chemistry (Appendix A)
 - c. Urinalysis
- 7. Adverse events
- 8. Record the usage of any concomitant medications and ongoing treatments.
- 9. Assessment of primary and secondary endpoints
- 10. Pregnancy test

8.8 Follow up visits at Day 45 (± 3 days) and Day 60 (± 3 days) (can be conducted via phone/teleconference)

- 1. Adverse events
- 2. Assessment of primary and secondary endpoints (observational assessment)

8.9 Subject Stopping Rules

If, in the opinion of the investigator, the participation in the study is or is becoming detrimental to the well-being of a particular subject, this issue should be discussed with the Medical Monitor for this study and dosing may be discontinued.

Subjects that experience a Grade 4 or greater toxicity according to the Common Terminology Criteria for Adverse Events (CTCAE) version 4 (https://evs.nci.nih.gov/ftp1/CTCAE/CTCAE 4.03 2010-06-14 QuickReference 5x7.pdf)

that is deemed to be possible, probably or definitely related to study drug will be discontinued from the study. Prior to discontinuation from the study, the grading of the event and causal relationship should be discussed with the Medical Monitor for the study.

Subjects will be discontinued from dosing if AST or ALT levels are >5 times the upper limit of normal, or if AST or ALT levels are >3 times the upper limit of normal along with a total bilirubin elevation of >2 times the upper limit of normal.

Subjects will be discontinued from dosing if Grade 3 diarrhea is observed.

Subjects will be discontinued from dosing if Grade 3 neutropenia is observed.

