8.10 Early Discontinuation of Study Treatment

A subject will be considered to have completed the efficacy portion of the trial if they received at least 21 days of treatment with study drug or the subject has been discharged from the hospital, or the subject has expired or the study is terminated by the sponsor. Subjects may prematurely discontinue study treatment for any of the following reasons:

- 1. Consent Withdrawn (specify the reason).
- 2. Significant and unacceptable adverse event specify the adverse event leading to discontinuation
- 3. Investigator decision (specify the reason), must be approved by the Medical Monitor
- 4. Non-compliance by subject with protocol requirements, must be approved by the Medical Monitor
- 5. Lost to follow-up (record the date of last contact)
- 6. Death (specify the following information)
 - a. Date of death
 - b. Death due to primary disease? Yes or no
 - c. Death due to study drug? Yes or no
 - d. Death due to adverse event? Yes or no
- 7. Study terminated by the Sponsor
- 8. Other reason (specify the reason) should be approved by the Medical Monitor

The reason for discontinuation of study treatment will be documented for each subject. Subjects who discontinue prematurely will not be replaced. If a subject is discontinued from the study, he will be asked to complete all End of Study visit assessments and return all study materials (study medication and electronic device). At the time of discontinuation, please fill out the End of Study case report forms (eCRFs) and subject disposition eCRF pages.

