8.11.1 Intensity of Adverse Events

The intensity of the AEs will be graded according to CTCAE version 4. For any adverse event that is not specifically covered in CTCAE version 4, the following criteria should be used:

Grade	Description
1	Mild; asymptomatic or mild symptoms; clinical or diagnostic observations only; intervention not indicated
2	Moderate; minimal, local or noninvasive intervention indicated; limiting age-appropriate instrumental activities of daily living
3	Severe or medically significant but not immediately life-threatening; hospitalization or prolongation of hospitalization indicated; disabling; limiting self-care activities of daily living
4	Life-threatening consequences: urgent intervention indicated.
5	Death related to AE

If the intensity (Grade) changes within a day, the maximum intensity (Grade) should be recorded. If the intensity (Grade) changes over a longer period of time, the changes should be recorded as separate events (having separate onset and stop dates for each grade).

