8.11.2 Test Medication Causality

The relationship (or association) of each AE to the test medication will be assessed by the investigator according to the following definitions:

Unrelated: There is no chance that the study medication caused the AE; other conditions, including concurrent illnesses, progression or expression of the disease state, or a reaction to a concomitant medication best explain the event.

Unlikely: There is little chance that the study medication caused the AE; other conditions, including concurrent illnesses, progression or expression of the disease state, or a reaction to a concomitant medication best explain the event.

Possible: The association of the AE with the study medication is unknown; however, the AE is not clearly due to another condition.

Probable: A reasonable temporal association exists between the AE and treatment administration and, based on the investigator's clinical experience, the association of the AE with the study treatment seems likely.

Definite: The association of the AE with the study medication has a direct relationship.

For the purpose of safety analyses, all AEs which are classified as "Possible," "Probable" or "Definite" will be considered treatment-related events.

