9.3.1 Primary Endpoint

The primary endpoint for the study will be the proportion of subjects that are alive without respiratory failure at Day 29. Respiratory failure is defined endotracheal intubation and mechanical ventilation, extracorporeal membrane oxygenation, high-flow nasal cannula oxygen delivery, noninvasive positive pressure ventilation, clinical diagnosis of respiratory failure with initiation of none of these measures only when clinical decision making is driven solely by resource limitation.

This analysis will compare the percentage of subjects that are alive without respiratory failure on Day 22 (responder). The percentage of subjects that meet these criteria in each of the two treatment groups will be summarized and compared observationally and statistically.

The number and percentage of responders will be summarized by treatment group. Responders will be analyzed using a logistic regression model. This model will include treatment as a factor and study site and WHO Ordinal Scale for Clinical Improvement at baseline as a covariates. Odds ratios, standard errors, 95% confidence intervals and p-values for the treatment difference will be presented.

The primary analysis will be performed on the ITT population. Subjects for whom respiratory failure and/or vital status at Day 29 cannot be established will be excluded from the analysis, noting that the number of such subjects is expected to be minimal. A sensitivity analysis will be performed treating these subjects as non-responders. A further sensitivity analysis also be performed on the mITT population.

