# 6.12.1 Primary Endpoint

QMD Ref: Worldwide-TMP-ST-005-7.0 Effective: 12Aug2019 Governing QMD: Worldwide-SOP-ST-		
Confidentiality Statement		
This document is the property of Worldwide Clinical Trials Inc. and may not be duplicated, copied, altered or removed from company without prior approval from Worldwide Quality Assurance or in compliance with Worldwide Standard Operating Procedures.		

REF: Worldwide-TMP-QA-001f-1.3

Worldwide Clinical Trials Controlled Quality Management Document		
WORLDWIDE CLINICAL TRIALS	Sponsor:	Veru Inc.
	Protocol Number:	V0211901
STATISTICAL ANALYSIS PLAN. PHASE 2-3-4		

The primary endpoint for the study is the proportion of subjects that are alive without respiratory failure at Day 29. Respiratory failure is defined as endotracheal intubation and mechanical ventilation, extracorporeal membrane oxygenation, high-flow nasal cannula oxygen delivery, noninvasive positive pressure ventilation, clinical diagnosis of respiratory failure with initiation of none of these measures only when clinical decision making is driven solely by resource limitation.

This analysis will compare the percentage of subjects that are alive without respiratory failure on Day 29 (responder).

Responders are subjects who have Grade 0-4 on the WHO Ordinal Scale for Clinical Improvement on Day 29. If subject was discharged from the hospital prior to Day 29 and WHO Ordinal Scale for Clinical Improvement is not collected at Day 29 then the last available observation before or at the time of discharge will be carried forward.

Non-responders are subjects who died before Day 29 or has Grade 5, 6, 7, or 8 on the WHO Ordinal Scale for Clinical Improvement on Day 29.

The number and percentage of responders will be summarized by treatment group. Responders will be analyzed using a logistic regression model. This model will include treatment as a factor, and study site, remdesivir use (No/Yes), dexamethasone use (No/Yes) and WHO Ordinal Scale for Clinical Improvement at baseline as a covariates. Odds ratios, standard errors, 95% confidence intervals and p-values for the treatment difference will be presented.

The primary analysis will be performed on the ITT population. A sensitivity analysis will be performed repeating the analysis on the EE population.

Example SAS code for the analysis is as follows:

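### Subjects taken off study for a related Grade 4 or greater toxicity while alive and still in hospital have no secured Day 29 status and no scoring rule in the SAP's primary analysis

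*Protocol*

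**What the plan says.** Protocol 8.9 attaches two different consequences to toxicity. For Grade 4 or greater events the rule is: "that is deemed to be possible, probably or definitely related to study drug will be discontinued from the study". For the others it is of the form "Subjects will be discontinued from dosing if Grade 3 diarrhea is observed" and "Subjects will be discontinued from dosing if Grade 3 neutropenia is observed", and the liver-enzyme rule likewise concerns dosing. Grading and causality must be discussed with the Medical Monitor before a Grade 4 removal.

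After removal, Protocol 8.10 says: "If a subject is discontinued from the study, he will be asked to complete all End of Study visit assessments". Protocol 8.6 makes the early-termination assessments the same as those of Day 22, including an endpoint assessment on that day. Protocol 8.11 follows a subject withdrawn for an adverse event until that event's outcome is known. Protocol 8.11.3 requires SAEs, including deaths, to be reported for 60 days from the start of dosing.

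On scoring, Protocol 9.3.1 says: "Subjects for whom respiratory failure and/or vital status at Day 29 cannot be established will be excluded from the analysis". It expects few such subjects and plans a sensitivity analysis that counts them as non-responders. SAP 6.12.1 defines a responder as WHO Grade 0-4 on Day 29 and carries a value forward only for subjects discharged earlier. For the rest: "Non-responders are subjects who died before Day 29 or has Grade 5, 6, 7, or 8 on the WHO Ordinal Scale". Its sensitivity analyses are a repeat in the EE population and a responder-rate comparison. SAP 6.12.2.6 repeats the primary analysis at Days 15 and 22.

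**The concern.** A subject removed under 8.9 while alive and in hospital has no guaranteed Day 29 grade and fits none of the SAP's scoring categories. A logistic model leaves out a record with no outcome, even though the population is labelled ITT.

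These subjects need not resemble the rest. The protocol's general Grade 4 criterion is "Life-threatening consequences: urgent intervention indicated". Causality of at least possible is enough for removal, and that category is defined as: "The association of the AE with the study medication is unknown; however, the AE is not clearly due to another condition". If the drug causes toxicity, removals would also be more frequent on VERU-111. Missingness could then depend on both treatment and outcome, and with 20 per arm each subject is 5% of an arm. Day 22 is exposed in the same way, and the protocol summary uses Day 22 responder status, together with tolerability, to decide on Phase 3. Scheduled safety contacts at Days 45 and 60 are not secured for these subjects either.

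**Working it through.** **Which subjects are affected.** The paths to Day 29 under SAP 6.12.1 are:

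| Situation at Day 29 | SAP 6.12.1 |
|---|---|
| Day 29 grade 0-4 | Responder |
| Day 29 grade 5-8 | Non-responder |
| Died before Day 29 | Non-responder |
| Discharged earlier, no Day 29 grade | Last value carried forward |
| Off study, alive, not discharged, no Day 29 grade | No rule |

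The wider carry-forward for otherwise missing records, in SAP 6.12.2.1, belongs to the secondary WHO-change endpoint. Neither of the SAP's sensitivity analyses of the primary endpoint scores a missing status. SAP section 9 lists the changes from the protocol; dropping the non-responder sensitivity analysis is not among them.

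**Scale.** The plan gives no power, response rate or Grade 4 rate, so there is no figure to reproduce. The only planned input is 20 + 20 = 40 subjects. Response counts and numbers removed below are assumptions.

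*Equal response, 14/20 in each arm (70%).* With k VERU-111 subjects removed, the difference should be 0 and becomes:

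| k | All failures: 14/(20−k) − 70% | All responders: (14−k)/(20−k) − 70% |
|---|---|---|
| 1 | 73.7 − 70 = +3.7 points | 68.4 − 70 = −1.6 |
| 2 | 77.8 − 70 = +7.8 | 66.7 − 70 = −3.3 |
| 3 | 82.4 − 70 = +12.4 | 64.7 − 70 = −5.3 |

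The standard error with nobody removed is √(2 × 0.7 × 0.3 / 20) = 14.5 points. In the worst case (all removals are VERU-111 failures, true response 70% in both arms), exact enumeration of the unadjusted Wald test with null variance gives a chance of a significant result favouring VERU-111 of 2.7% for k = 0, then 5.9%, 10.2% and 16.8% for k = 1, 2, 3.

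*16/20 versus 11/20, two VERU-111 subjects removed.* The statistic is z = (p1 − p2)/√[p(1−p)(1/n1 + 1/n2)], with p the pooled rate. The two-sided Barnard p-value is maximised over the common rate with arm sizes fixed. The SAP's example code for the responder-rate analysis requests Barnard's test.

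| Removed | VERU-111 | Difference from 11/20 = 55% | z | Barnard p |
|---|---|---|---|---|
| None | 16/20 = 80.0% | +25.0 points | 1.69 | 0.107 |
| Two failures | 16/18 = 88.9% | +33.9 | 2.30 | 0.023 |
| One of each | 15/18 = 83.3% | +28.3 | 1.88 | 0.074 |
| Two responders | 14/18 = 77.8% | +22.8 | 1.48 | 0.16 |

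If the same two subjects are instead scored as non-responders, the denominator returns to 20. The differences are 16/20 − 55% = +25, 15/20 − 55% = +20 and 14/20 − 55% = +15 points. Scoring as non-response therefore cannot inflate the VERU-111 rate, but it understates it when a removed subject was in fact a responder.

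**The case against.** Several points on the other side stand.

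- Deaths do not drop out: the SAP counts them as non-responders, and they are reportable for 60 days. Discharged subjects are scored. The group at risk is narrow.
- Exclusion is not automatic. Protocol 9.3.1 excludes only subjects whose status cannot be established. Event follow-up, SAE reports and the exit endpoint assessment may establish some statuses, especially if the event is an unresolved respiratory deterioration. None of them guarantees a Day 29 grade.
- A reader might infer that ordinary COVID-19 deterioration to intubation would routinely trigger removal before it is scored. The documents do not support that. An event best explained by disease progression is classed as unrelated or unlikely, the possible category requires that no other condition is clearly the cause, the Medical Monitor discusses each case, and the trial is double-blind. It can happen, but it is not the rule's normal effect.
- A reader might also infer that the gap inflates the VERU-111 result or could by itself decide Phase 3. The inflated figures need every removed subject to be a VERU-111 failure, and mixed removals look different. The Phase 3 decision rests on a clinically relevant Day 22 difference and on tolerability, not on a Day 29 p-value. Related Grade 4 events would themselves count against tolerability.
- The primary analysis is a covariate-adjusted logistic model, which the unadjusted figures only approximate.

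One could add that 8.10, headed as stopping study treatment, also speaks of discontinuation from the study, so 8.9 may have meant dosing only. That is a reason to reconcile the wording, since 8.9 repeats the off-study phrase in its next sentence and uses dosing language elsewhere.

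**Conclusion.** The point holds as a gap in follow-up and scoring. Followed as written, the plan can leave a subject with a related Grade 4 or greater toxicity without a Day 15, 22 or 29 status, depending on when removal occurs. The SAP does not say how to count that subject, and the protocol's safeguard has disappeared without being recorded as a change.

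The size and direction of any bias are unknown. Under the assumed counts, two lost VERU-111 subjects move a 25-point difference to anywhere from about 23 to 34 points, and only the case where both are failures takes Barnard's p below 0.05. With no true effect, one to three lost failures give +3.7 to +12.4 points, below the standard error of about 14 points. If removals are unrelated to arm and outcome, the main cost is lost precision. The change is worth making because the loss may be informative, each subject is 5% of an arm, and the correction is small.

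**What to change.** 1. Protocol 8.9: reconcile the off-study and off-dosing wording with 8.6, 8.10 and 8.11. No view is taken here on the dosing rule itself.
2. State that, whatever happens to dosing, endpoint status at Days 15, 22 and 29 and the Day 45 and 60 safety contacts are still collected unless the subject withdraws consent.
3. SAP 6.12.1 and 6.12.2.6: score as a non-responder any ITT subject whose status at the visit cannot be established and who is not covered by the discharge carry-forward, whatever the reason for leaving. This also covers consent withdrawal and loss to follow-up. Report the protocol's exclusion approach as a sensitivity analysis, and record the change in SAP section 9.
4. At minimum, restore the non-responder sensitivity analysis of Protocol 9.3.1 to the SAP.

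The cost is a few sentences and a few more follow-up contacts. The visits already exist, and Days 45 and 60 may be done by phone. The responder rate becomes slightly conservative, more so in an arm with more missing statuses, and the exclusion analysis would show by how much.

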7.0 STUDY MEDICATION

7.1 Enrollment and Blinding

The study will be a randomized, double-blind, placebo-controlled study. The study will be unblinded when the last patient has completed the Day 29 assessments.

An emergency code break will be available to the investigator / pharmacist / investigational drug storage manager. This code break option in IWRS may only be disclosed in emergency situations when the identity of the trial drug must be known to the investigator in order to provide appropriate medical treatment or if required to assure safety of trial participants. If the code break for a patient is opened, the sponsor and CRO will be informed immediately via IWRS notification. The reason for the IWRS unblinding of the subject must be documented on the appropriate eCRF page along with the date and the initials of the person who broke the code.

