 Plasma samples for pharmacokinetic assessment will be taken at baseline (prior to dosing on Day 15) and at 4 hours (±2 hours), 12 hours (±2 hours) after dosing on Day 15, and at 24 hours (±2 hours) after dosing on Day 15 (prior to dosing on Day 16). (Day 15 only)

8.6 Day 22 ± 3 days (these assessments will also be done at Early Termination or Discontinuation from the study)

The following assessments will be performed on Day 22 (\pm 3 days):

- 1. Vital Signs (temperature/pulse/supine blood pressure)
- 2. SpO₂
- 3. Physical examination (including weight)
- 4. 12-lead ECG (single)
- 5. Chest X-ray or CT scan
- 6. Clinical Laboratory tests
 - a. Hematology (Appendix A)
 - b. Serum chemistry (Appendix A)
 - c. Urinalysis
- 7. Adverse events
- 8. Record the usage of any concomitant medications and ongoing treatments.
- 9. Assessment of primary and secondary endpoints

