8.11 Adverse Events

An adverse event (AE) is any unfavorable or unintended change in body structure (signs) or body function (symptoms), abnormal laboratory result that is associated with symptoms or requires treatment or worsening of a pre-existing condition. This includes all such events regardless of the presumed relationship between the event and the study medication(s).

Any AE that occurs after the informed consent is signed but prior to dosing on Day 1 will be captured as part of the medical history and will be documented on the appropriate eCRF. This would include AEs resulting from concurrent illnesses, reactions to concomitant medications or progressive disease states. These AEs will be captured as part of the medical history.

Each subject will be assessed for the development of any adverse events. Adverse events should be assessed at each visit to the clinic. This information should be obtained in the form of non-leading questions (e.g., "How are you feeling?") and from signs and symptoms detected during each examination, observations of the study personnel or spontaneous reports from the subjects.

Any AEs such as complaints, signs, or symptoms that occur during the course of the study or designated follow-up periods will be recorded on the subject's case report form (eCRF). This would include AEs resulting from concurrent illnesses, reactions to concomitant medications, or progressive disease states.

Whenever possible, the AE will be described on the case report form using standard medical terminology consistent with Common Terminology Criteria for Adverse Events (CTCAE) version 4 in order to avoid the use of vague, ambiguous or colloquial expressions. The investigator will evaluate all adverse events as to their intensity, relation to test medication, outcome and action taken.

Each AE will be evaluated for duration, intensity, and relationship to (or association with) the study treatment (or other causes). Additionally, the actions taken (e.g., reduction of dosage, discontinuation of study medication, administration of treatment, etc.) and the resulting outcome of the AE will be indicated on the case report form.

Any subject who is withdrawn from the study due to an adverse event will be followed until the outcome of the event is determined, and the investigator will prepare a written summary of the event and document the available follow-up information on the case report form.

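### Subjects removed for related Grade 4 or greater toxicity need not be assessed at Day 29, and the SAP omits the protocol's rule for unknown Day 29 status

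*Protocol*

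**What the plan says.** **Stopping rules.** Protocol 8.9 treats toxicities in two ways. Subjects with a Grade 4 or greater event judged at least possibly "related to study drug will be discontinued from the study". The other rules are confined to dosing: "Subjects will be discontinued from dosing if Grade 3 diarrhea is observed", and the liver-enzyme and Grade 3 neutropenia rules are worded the same way.

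**What is collected on leaving.** The heading of Protocol 8.6 (the Day 22 visit) states that "these assessments will also be done at Early Termination or Discontinuation from the study", and item 9 of that visit is "Assessment of primary and secondary endpoints". Protocol 8.10 adds: "If a subject is discontinued from the study, he will be asked to complete all End of Study visit assessments". Section 8.14 asks for the final-visit evaluations at withdrawal, and Appendix B, footnote d, equates early termination with Day 22. On safety, 8.11 says: "Any subject who is withdrawn from the study due to an adverse event will be followed until the outcome of the event is determined". Section 8.11.3 makes deaths from any cause reportable for 60 days after dosing starts.

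**Unknown Day 29 status.** Protocol 9.3.1 excludes subjects whose respiratory or vital status at Day 29 cannot be established, expects few of them, and specifies a sensitivity analysis that counts them as non-responders. SAP 6.12.1 defines responders by a WHO grade of 0 to 4 on Day 29, and non-responders by death before Day 29 or a grade of 5 to 8 on Day 29. It carries a grade forward only for subjects discharged from hospital before Day 29.

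**The concern.** Because 8.9 separates leaving the study from stopping the drug, a site that follows it literally will stop collecting respiratory status after a related Grade 4 event. Removal then follows toxicity attributed to treatment, which is an unsafe reason for an outcome to go missing.

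Unequal loss between arms is possible, not established. Protocol 7.1 says: "The study will be a randomized, double-blind, placebo-controlled study". Causality is therefore judged blinded, and 8.11.2 defines a possible relationship broadly: "The association of the AE with the study medication is unknown; however, the AE is not clearly due to another condition". Placebo subjects can be removed too. If losses do differ, leaving these subjects out weakens the comparison of all randomized subjects, and the bias can go either way.

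The SAP gap is wider than 8.9. It covers unknown Day 29 status from any cause, including withdrawn consent and loss to follow-up. The 8.9 wording adds one avoidable cause. Without the protocol's sensitivity analysis, a reader cannot see how far the result depends on these subjects.

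**Working it through.** **1. Each possible Day 29 position against the two documents**

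| Position | SAP 6.12.1 | Protocol 9.3.1 |
|---|---|---|
| Grade 0–4 on Day 29 | Responder | Responder |
| Grade 5–8 on Day 29 | Non-responder | Non-responder |
| Died before Day 29 | Non-responder | Non-responder |
| Discharged before Day 29, no Day 29 grade | Last grade up to discharge carried forward | Excluded if status cannot be established; non-responder in sensitivity analysis |
| Alive, no recorded discharge, no Day 29 grade | No rule | Excluded; non-responder in sensitivity analysis |

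Grade 5 events are deaths and already count as failures, so under 8.9 the last row concerns surviving Grade 4 cases. The early-termination visit records the endpoint on the day of leaving, which gives Day 29 status only if the subject leaves near Day 29.

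**2. Whether another part of the SAP fills the last row**

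- SAP 6.12.2.1 carries forward grades missing for other reasons, but for the mean-change secondary endpoint; 6.12.1 does not refer to it.
- The efficacy-evaluable analysis changes the population, and the Wald and Barnard analysis changes the test. Neither addresses missing outcomes.
- Primary-endpoint tables 14.2.1.1 to 14.2.1.4 include no missing-as-non-responder output.
- SAP section 9 lists other departures from the protocol, but not this one.

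**3. Size for one subject**

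The plan has no figure to reproduce: Protocol 9.1 and SAP section 4 state that no power calculation was done, and no response rates are given. The 20 per arm comes from Protocol 6.1. The true responder counts, 16/20 VERU-111 and 14/20 placebo, are assumptions. One subject is 1/20 = 5.0 points.

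Difference = p(VERU-111) − p(placebo). Odds ratio (OR) = odds(VERU-111) / odds(placebo).

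With no data missing: 80.0% − 70.0% = +10.0; OR (16/4)/(14/6) = 1.71.

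| One survivor unknown | Excluded | Counted as non-responder |
|---|---|---|
| VERU-111, true failure | 16/19 = 84.2%; +14.2, OR 2.29 | 16/20 = 80.0%; +10.0, OR 1.71 |
| VERU-111, true responder | 15/19 = 78.9%; +8.9, OR 1.61 | 15/20 = 75.0%; +5.0, OR 1.29 |
| Placebo, true failure | 14/19 = 73.7%; +6.3, OR 1.43 | 14/20 = 70.0%; +10.0, OR 1.71 |
| Placebo, true responder | 13/19 = 68.4%; +11.6, OR 1.85 | 13/20 = 65.0%; +15.0, OR 2.15 |

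Counting unknowns as failures is thus conservative only for VERU-111 losses.

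Gap between the two rules in the affected arm:

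- True rate 60%: 12/19 − 12/20 = 3.2 points, or 11/19 − 11/20 = 2.9.
- True rate 90%: 18/19 − 18/20 = 4.7 points, or 17/19 − 17/20 = 4.5.

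Over true rates of 60% to 90% the gap is therefore 2.9 to 4.7 points.

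**4. Size for two subjects, adding carry-forward**

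Assume placebo is complete at 12/20, and VERU-111 has 16 responders among 18 known and two unknown. The test uses the null variance, as in the SAP's example code for the responder-rate analysis: z = (p1 − p2) / √[p(1 − p)(1/n1 + 1/n2)], with p the pooled rate.

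| Rule | VERU-111 | Difference | Two-sided p |
|---|---|---|---|
| Excluded | 16/18 | +28.9 | 0.043 |
| Non-responders | 16/20 | +20.0 | 0.168 |
| Carried forward as responders | 18/20 | +30.0 | 0.028 |

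Fisher's exact test on the same tables gives 0.067, 0.301 and 0.065, so whether the 5% level is crossed also depends on the test. All figures in steps 3 and 4 are unadjusted; the planned model gives an adjusted odds ratio.

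**The case against.** The strongest reply is that 8.9 is the weaker half.

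- **Loose wording.** Section 8.10 is titled as discontinuation of treatment yet speaks of leaving the study, so 8.9 may be equally loose.
- **Data continue.** There is an endpoint assessment on leaving, the event is followed to its outcome, and a life-threatening event is reportable as serious. Some affected subjects would still be inpatients at Day 29, with status recoverable from hospital records.
- **Few subjects.** The protocol expects few unknowns, and this is an unpowered proof-of-concept trial.
- **The SAP gap is partly nominal.** The SAP says it is based on the protocol, and a logistic model normally drops missing outcomes, which would reproduce the protocol's exclusion. On that view only one sensitivity table is lost.
- **The remedy is inconsistent.** It restores an exclusion that itself weakens the all-randomized comparison.

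The small expected number stands, as do the likelihood of exclusion by default and the limited use of amending 8.9 now. The rest does not remove the problem. No text requires Day 29 respiratory status after removal, and possible recovery from records is not a plan to collect it. The SAP never states that exclusion applies, and its carry-forward wording for a neighbouring endpoint leaves a third choice open. Restoring exclusion does not cure the missing data, which is why follow-up comes first and the sensitivity analysis must accompany the exclusion.

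**Conclusion.** The concern holds. Read as written, the protocol can lose Day 29 respiratory status after related Grade 4 toxicity. The SAP then has no stated rule for such a subject, or for any other survivor with no recorded discharge and no Day 29 grade. It also omits a protocol-specified sensitivity analysis without declaring the omission.

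The effect depends on a count that the documents do not give. If it is zero, the primary result is untouched. Otherwise, for one such subject and true rates of 60% to 90%, excluding the subject and counting a failure differ by 2.9 to 4.7 points in the affected arm. This should be corrected because correction is cheap and the choice belongs in the plan. Confidence is medium: neither the number of removals nor their balance between arms is known.

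**What to change.** **Protocol 8.9.** Make the related Grade 4 or greater rule a stop to dosing, like its neighbours. Keep collecting respiratory and vital status at Days 15, 22 and 29, and adverse events to Day 60, by phone if needed, unless consent is withdrawn. This costs a wording amendment and a few contacts at visits that already exist. It helps only subjects whose follow-up is still open; SAP section 9 says all randomized subjects had been treated, so it may come too late here.

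**SAP 6.12.1, before database lock.** State that subjects with unknown Day 29 status are excluded from the primary analysis, and add the sensitivity analysis counting them as non-responders. Report their number by arm and reason, even if it is zero. List any intended departure from Protocol 9.3.1 in SAP section 9. The cost is a short text change and one extra table. The documents give no lock date, so the time remaining needs checking.
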